5.2 Primary Efficacy Endpoint(s)

5.2.1 Definitions

Six-point ordinal clinical recovery scale

The 6-point ordinal clinical recovery scale (CRS) provides 6 mutually exclusive conditions ordered from best to worst, and the score reflects the participant's worst situation on the day of the assessment:

1. Not hospitalized
2. Hospitalized, not requiring supplemental oxygen
3. Hospitalized, requiring low flow supplemental oxygen
4. Hospitalized, on non-invasive ventilation, nonrebreather mask or high flow oxygen device
5. Hospitalized, on IMV or ECMO
6. Death

The CRS can be derived from baseline up to and including day 28. The CRS will be missing after trial discontinuation if the participant discontinued the trial for other reason than death. Participants who die before day 28 (before or after discharge from hospital) will be considered to continue the trial up to and including day 28.

The CRS categories are defined below. For ease of categorization, the categories are defined from worst to best. A participant will be evaluated in the same ordering of the categories as below. Once a participant fulfils the criteria for a category, the category is assigned to the participant and the evaluation stops.

6. Death
 - o Participant died at any time on the day of assessment or earlier (all-cause mortality).
5. Hospitalized, on IMV or ECMO

- o IMV or ECMO is used at any time on the day of assessment, OR
- o From a Medical Perspective, the participant should have been on IMV on the day of the assessment

4. Hospitalized, on non-invasive ventilation, nonrebreather mask, or high flow oxygen device
 - o The participant is on supplemental oxygen and the worst FiO₂ is $\geq 50\%$.
3. Hospitalized, requiring low flow supplemental oxygen
 - o On supplemental oxygen with worst FiO₂ $< 50\%$ and the participant was not able to sustain a blood oxygen saturation of $> 93\%$ when breathing room air, OR
 - o Not on supplemental oxygen and the minimum of all available SpO₂ values during the day is $\leq 93\%$
2. Hospitalization, not requiring supplemental oxygen
 - o Hospitalized according to the status described below
1. Not hospitalized, including subjects on low level of oxygen

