5.3.2 Key Secondary Estimands

Clinical improvement at Day 28

Population: The population of interest are hospitalized patients between ≥ 18 and <85 years old with confirmed critical COVID-19 disease.

Endpoint: Sustained clinical improvement at Day 28 (yes/no)

Interventions: Received Sirukumab 5 mg/kg (IV single dose infusion on Day 1) and placebo (IV infusion on Day 1), both on top of SOC.

Intercurrent Events:

- Death as intercurrent event is handled in a composite strategy as it is the worst category on the clinical scale. Participants that died at Day 28 or earlier will be considered as failure (Sustained clinical improvement at Day 28=no), irrespective of whether a clinical improvement occurred prior to death.
- The intercurrent event of the use of prohibited medication is handled in a treatment policy strategy: data will be used as observed.
- The intercurrent event of discharge to the alternate care settings ‘different hospital’, ‘acute care facility’, ‘subacute care facility’ or ‘hospice/palliative discharge’ is handled in a while on treatment strategy: see section 5.2.1
- Participants that discontinue the study before Day 28 will be considered as failure (Sustained clinical improvement at Day 28=no), unless they had an event of sustained clinical improvement prior to discontinuation. In the latter scenario it will be considered a success (Sustained clinical improvement at day 28=yes).

Population-level summary measure:

The difference in proportion of participants with of ‘Sustained clinical improvement at Day 28’ for experimental treatment versus placebo.

All-cause mortality up to Day 28

Population: The population of interest are hospitalized patients between ≥ 18 and <85 years old with confirmed critical COVID-19 disease.

Endpoint: Death by Day 28 (Yes/No)

Treatment: Sirukumab 5 mg/kg (IV single dose infusion on Day 1) and placebo (IV infusion on Day 1), both on top of SOC.

Intercurrent events:

- The intercurrent event of the use of prohibited medication is handled in a treatment policy strategy: data will be used as observed.
- Participants that discontinue the study before Day 28 with a score > 1 on the CRS will be analyzed according to the composite strategy and will be considered as death on day 28 (Death by day 28=yes).

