| Time to Mechanical Ventilation (up to Day 28) (days) among participants not on mechanical ventilation at Baseline [Time-to event] | Similar as for the primary endpoint, but with a score of 5 on the CRS (instead of an improvement of 2 categories). Participants who did not evolve to score 5 and who die will be censored at the day of death. This endpoint will be evaluated in the subgroup of participants for which the CRS is less than 5 at Baseline. |
| Time from study intervention to ICU discharge (up to Day 28) among the participants on ICU at baseline (days) [Time-to event] | Subjects who die at or before day 28 will be censored on day 28. Subjects alive on day 28: Only ICU periods with a starting day \leq day 28 are taken into account. Missing end dates of ICU periods are imputed with the cut-off date (for ongoing subjects) or the date of study discontinuation/completion - If last ICU stay end date $<$ minimum(date visit day 28, study discontinuation, study completion), -> the subject has an event on the last day in the ICU + 1 day. - If last ICU stay end date \geq minimum (date visit day 28, study discontinuation, study completion), -> the subject will be censored on minimum(day 28, day study discontinuation, day study completion). |
| Total length of hospitalization among the surviving participants (up to Day 28) (days) [Duration] | The total number of days a subject stayed in the hospital during the period from study drug intake until day 28, calculated as sum of the individual hospitalization periods, including re-hospitalizations. This endpoint will be evaluated in the subgroup of participants who were still alive at day 28 The total length of hospitalization will be missing for participants who discontinue the trial for other reason than death before day 28. |
| Number of ventilation free days in participants on IMV/ECMO at baseline (up to Day 28) (days) [Duration] | Calculated as: Date day 28 – maximum date of day with score ≥ 5 Participants who die will be considered as being on IMV/ECMO until day 28. |

| | |
|---|--|
| Improvement at day 28 on the CRS with at least 1 category at day 28 (or at discharge/discontinuation) [Incidence] | CRS improved with at least 1 category at day 28 (or at discharge/discontinuation) when compared to baseline (Yes/No) |

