| Improvement at day 28 on the CRS (As observed) with at least 2 categories at day 28 (or at discharge/discontinuation) [Incidence] | The CRS (As observed) improved with at least 2 categories at day 28 (or at discharge/discontinuation) when compared to baseline (Yes/No) |
| CRS worsening relative to Baseline (up to Day 28) [Incidence] | CRS worsened with at least 1 category between day 5 and day 28 (Yes/No) |
| Ventilation free survival at Day of Discharge/Day 28 [Incidence] | CRS score 1, 2, 3 or 4 at Day 28. Participants with a missing score at Day 28 will not be considered |
| CRS at Day 7, 14, 21 and 28 [Proportions] | See section 5.2.1. |

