ATTACHMENT 3. CRS DERIVATION

The CRS categories should be evaluated from 6 to 1. First check if the subject falls in category 6 (has the subject died?) if not then we evaluate category 5, if not 5 then evaluate category 4 and so on.

The CRS is evaluated at baseline and per day, relative to the start of the study drug intake. The baseline CRS is based on the data obtained at the time of randomization.

Notes:

- The CRS scores will be calculated up to day 28 for subjects who are still in the trial at day 28. Participants who die before they discontinued the trial before day 28 will be considered to continue the trial up to and including day 28.
- If the subject has different types of oxygen supplementation on a single day, the worst type will be considered to derive the score.
- In case the subject withdrew from the study for other reason than death, the CRS will not be calculated from the next day onwards. A record indicating this type of missing scores should be foreseen in the ADAM data sets.
- Intermittent missing values can occur (eg. Due to incomplete supplementary oxygen information). For intermittent missing values, a record should be foreseen in the adam dataset. It should be possible to make the distinction between this type of missing values and the missing values due to trial discontinuation.

Hospitalized and Not Hospitalized

Rules will be applied in the order as described below. The first rule fulfilled by a subject will be considered.

1. If a subject is discharged to the alternate care settings “2. Different hospital”, “3. Acute Care Facility”, “4. Subacute care facility” or “7. Hospice/Palliative Discharge”, the subject will be considered hospitalized until day 28 or until trial discontinuation. The subject will be categorized in the category the subject was in at the moment of discharge.
2. If a subject is discharged ‘against medical advice’, the subject will be considered hospitalized on the day of discharge and on the day after discharge (unless the subject discontinued the trial). The subject will be categorized in the category the subject was in at the moment of discharge. The CRS will be considered missing on subsequent days.

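### Ventilation-free days have no rule for participants last seen on the ventilator and then unobserved, so the formula counts their unobserved days as ventilation-free

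*SAP*

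**What the plan says.** The ventilation-free-days row of SAP 5.4.1 applies to participants on invasive mechanical ventilation (IMV) or ECMO at baseline. The value is the Day 28 date minus the "maximum date of day with score" of 5 or higher. The row's one exception is: "Participants who die will be considered as being on IMV/ECMO until day 28".

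Two provisions determine what the formula sees after a participant leaves. SAP 5.2.1 states: "The CRS will be missing after trial discontinuation if the participant discontinued the trial for other reason than death". Attachment 3 adds that after such a withdrawal "the CRS will not be calculated from the next day onwards". Separately, after discharge against medical advice the category at discharge is kept for that day and the next, and the CRS is missing from then on.

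Nearby rows of SAP 5.4.1 do deal with early departure:
- Length of hospitalization: "The total length of hospitalization will be missing for participants who discontinue the trial for other reason than death before day 28".
- Time to end of oxygen supplementation and time to ICU discharge: censored at discontinuation.
- Ventilation-free survival: "Participants with a missing score at Day 28 will not be considered".

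SAP 5.4.2 restricts both the descriptive statistics and the Hodges-Lehmann comparison of ventilation-free days to participants alive at Day 28. Protocol 9.4.4 names a stratified Wilcoxon rank-sum test for this endpoint and gives no rule for discontinuation.

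**The concern.** The formula subtracts dates; it does not count days on which the participant was seen off the ventilator. When the record stops while the participant is at score 5, the last day at 5 or above is simply the last day of observation. The remaining days to Day 28 are unknown, but the subtraction treats them as free of ventilation. The participant then has the same value as someone extubated on that day and followed off the ventilator to Day 28.

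This is more than a missing detail, because the stated rule, applied literally, returns a specific and unsupported number. Two programmers could also treat the same record differently: as 22, as 0, as missing or as excluded. At stake is the credibility of a listed secondary endpoint in what is probably a small subgroup, where a few such records could matter.

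**Working it through.** The plan gives no figure for this endpoint, so there is none to reproduce. The check applies the stated rule to example records.

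**Inputs.** Formula and death exception: SAP 5.4.1. CRS missing after leaving alive: SAP 5.2.1 and Attachment 3. Carry-forward after transfer to another hospital, and the rule for discharge against medical advice: SAP 5.2.1, hospitalization status.

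**Formula.** Ventilation-free days = 28 − last study day with a non-missing CRS of 5 or more. Let *d* be the last day in hospital at score 5, or the day of departure.

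- Leaves the trial alive on day *d*: 28 − *d*
- Extubated after day *d* and observed off the ventilator to Day 28: 28 − *d*
- Discharged against medical advice on day *d*: score 5 is kept through *d* + 1, so 28 − (*d* + 1)
- Transferred to another hospital on day *d* and in the trial to Day 28: score 5 carried forward, 28 − 28 = 0
- Dies on day *d* + 1: 28 − 28 = 0

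| *d* | Leaves trial alive | Extubated and observed | Against medical advice | Transferred | Dies |
|---|---|---|---|---|---|
| 2 | 26 | 26 | 25 | 0 | 0 |
| 5 | 23 | 23 | 22 | 0 | 0 |
| 6 | 22 | 22 | 21 | 0 | 0 |
| 10 | 18 | 18 | 17 | 0 | 0 |
| 20 | 8 | 8 | 7 | 0 | 0 |

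The first two result columns agree on every row, so the formula cannot distinguish an unobserved participant from a recovered one. Transfer while ventilated is already handled by carry-forward and is not part of the problem.

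**Does the restriction to participants alive at Day 28 remove these records?** Not clearly, for three reasons.
1. Length of hospitalization has the same restriction and still carries its own discontinuation sentence. If being alive at Day 28 excluded discontinuers, that sentence would have no work to do.
2. The ICU-discharge row divides participants into those who die by Day 28 and those alive on Day 28, and handles early discontinuation under the second group.
3. The SAP does not say how unknown Day 28 vital status is classed.

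**Does the mortality imputation remove them?** SAP 5.3.2 counts as deaths "Participants that discontinue the study before Day 28 with a score > 1 on the CRS", but states this only for the all-cause mortality estimand. SAP 5.4 does not refer to it.

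**Scale, under assumptions.** The documents give no number of participants on IMV/ECMO at baseline. If an arm had 10 to 20 analysed participants, one record scored 22 instead of 0 would move that arm's mean by 22/10 = 2.2 to 22/20 = 1.1 days. This concerns the descriptive mean only.

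**The case against.** The strongest reply is that almost nobody can reach the analysis this way. Protocol 7.2 lists three reasons for withdrawal: loss to follow-up, withdrawn consent and death. Protocol 7.3 ties loss to follow-up to the phone visits, so it does not describe a ventilated inpatient. Withdrawn consent is the realistic way to leave the trial on a ventilator, but the Day 28 call (Schedule of Activities, footnote n) is not made to those who withdrew consent, and Protocol 7.3 keeps later vital status out of the eCRF. Such a participant has no recorded Day 28 status and might never be classed as alive.

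Most of this stands: a ventilated discontinuer with a recorded Day 28 alive status should be rare. It does not close the gap. The SAP leaves unknown status unclassified, and the ICU-discharge row suggests that discontinuers may count as alive. Deferred consent (Protocol 4.2.1) gives a plausible route to withdrawal while ventilated. Discharge against medical advice does not require leaving the trial, so the Day 28 call can still record the participant alive. Score 5 is also assigned to someone who medically should have been on IMV but was not, so leaving hospital at score 5 is possible.

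Two further replies are sound. Both the Hodges-Lehmann comparison in the SAP and the protocol's Wilcoxon test are rank-based, so one extreme value has limited influence. Different endpoints may also use different strategies, so counting a discontinuer as a death in the mortality estimand does not by itself contradict another treatment here.

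**Conclusion.** The ventilation-free-days rule gives an unsupported value for a participant whose last observed score is 5 or more, whose later scores are missing, and who is not classed as dead. The error for such a record can be as large as the whole unobserved period, for example 22 days when the last ventilated day is 6. Whether any such record enters the analysis depends on how alive at Day 28 is defined, which the SAP leaves open. Few participants are likely to be affected, and no primary or key secondary conclusion depends on this endpoint.

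A reader might infer more than the documents support:
- That the planned comparison sets 22 days for a discontinuer against 0 for a participant who dies. It does not, because SAP 5.4.2 excludes deaths by Day 28.
- That the treatment estimate would shift by 1.1 to 2.2 days. Those are mean shifts with assumed arm sizes and an assumed true value of 0; the effect on the Hodges-Lehmann estimate was not computed.
- That one arm is favoured. The documents give no basis for expecting more such departures in either arm.

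**What to change.** Add one sentence to the ventilation-free-days row of SAP 5.4.1, using the approach already adopted for length of hospitalization. The value is missing for any participant who leaves the trial before Day 28 for a reason other than death, and for any participant whose CRS is missing through Day 28 after discharge against medical advice. This treats participants last seen on and off the ventilator alike. Scoring the first group 0 and dropping the second would keep poor values and discard good ones, and would depart from the neighbouring rule.

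A sensitivity analysis may count those with a last CRS of 5 or more as 0 days, since leaving while ventilated is unlikely to be unrelated to outcome.

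The cost is one sentence, and the loss of a few records from an already small subgroup. No change to data collection is needed.

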5.4.2 Analysis Methods

The secondary endpoint evaluation will be conducted on the primary and on the ITT population.

Time-to event parameters

The time-to-event parameters will be evaluated based on the log-rank test, stratified for the stratification factors (age [<65 and ≥ 65 years] and use of IMV [yes/no]). The tests will be performed 1-sided at a 5% significance level. The actual values of the stratification factors will be used, not as randomized.

Cumulative proportion of patients with an event, by treatment, will be provided using the complement of the Kaplan Meier curve. The analyses will be completed with the median time to event (if reached) and the proportion of participants who with an event on day 7, 14, 21 and 28; all per Kaplan Meier method. The complementary log-log transform method is used to calculate the 90% confidence intervals.

Duration parameters

Descriptive statistics of the duration parameters will be shown for all participants that were still alive at day 28.

Total length of hospitalization and number of ventilation free days will be analyzed in the subgroup of participants that were still alive at day 28 by using the Hodges-Lehman approach. Corresponding 90% CIs will be presented as well.

Incidence parameters

For each parameter the number and percentage of participants in each category and subcategory will be tabulated and listed. All participants in the applicable analysis set will be counted for the denominator of the proportion.

The occurrence (yes/no) as described for the incidence parameters will be analyzed using logistic regression as described above (section 5.3).

Proportions: CRS outcome and CRS (As observed) outcome

A tabulation will be made of the CRS and CRS (As observed) outcomes at each day, taking only non-missing values into account (i.e.: the percentages of the six categories per day should sum up to 100%).

A proportional odds model will be used as model to analyze the CRS and CRS (As observed) on days 7, 14, 21 and 28, modeling the common odds ratio of improvement on the ordinal scale of active treatment versus placebo using the 6-point CRS (scores 1.2 and 1.1 will be pooled into a single category 1) The model will include treatment, CRS at baseline (≤ 3 vs > 3) and the stratification factors. The proportional odds assumption in the treatment effect will be tested in a model that includes both separate slopes and common slopes for treatment. In case the validity of this model is questionable (eg. due to quasi-complete separation of data points), categories on the CRS will be merged (eg. category 2 with category 1). If the assumption of the proportional odds is acceptable, in a first step equal slopes (i.e. proportional odds) for the treatment effect only and unequal slopes for the other covariates, will be modeled. If this model cannot be estimated, a full proportional odds model will be applied, i.e. implying proportional odds for all covariates in the model. The common odds ratio from the final model will be considered as the estimate of the treatment effect. The actual values of the stratification factors will be used for all models, not as randomized. The proportional odds model will be defined in such a way that a common odds ratio smaller than 1 indicates larger improvement in the active treatment group.

If the assumption of the proportional odds would not hold for the treatment effect, the Van Elteren test will be used in a sensitivity analysis and the resulting p-value would be used in the formal testing.

Graphical displays and tabulations will be provided showing the proportion of subjects per CRS category and day. Also, shift tabulations will be provided of the CRS category over time versus the baseline CRS category

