To evaluate the clinical response of sirukumab + SOC compared to placebo + SOC in confirmed (a) critical and (b) severe or critical COVID-19 disease	
 Time to improvement^a of at least 1 category relative to Baseline on the 6-point ordinal clinical recovery scale (up to Day 28) Proportion of participants with an improvement on Day 28 of at least 1 category relative to Baseline on the 6-point ordinal clinical recovery scale Time from study intervention to end of oxygen supplementation (up to Day 28) Time from study intervention to hospital discharge among the surviving participants (up to Day 28) Total length of hospitalization among the surviving participants (up to Day 28) Number of ventilation free days (up to Day 28) Participant's clinical status at Day 7, 14, 21, 28 (6-point ordinal clinical recovery scale) Total time on invasive mechanical ventilation Proportion of participants with a worse^b category relative to Baseline on the 6-point ordinal clinical recovery scale (up to Day 28) Proportion of participants on extracorporeal membrane oxygenation (ECMO) over time Total time on ECMO
To evaluate the safety during follow-up for (a) critical and (b) severe or critical COVID-19 disease	
 Proportion of alive participants at Day 28, Week 8, and Week 16 Proportion of alive participants that required readmission at Week 8 and Week 16 (if previously discharged) Incidence of SAEs up to Week 16
Exploratory	
To evaluate biomarkers that may be associated with response to or complications of sirukumab treatment	Evaluations may include, but are not limited to, IL-6, procalcitonin, C-Reactive protein (CRP), ferritin, LDH and D-dimer serum concentrations (through Day 28)
To explore changes in SARS-CoV-2 viral load and viral genome	
 Time to SARS-CoV-2 undetectable viral load by RT-PCR (up to Day 28) SARS-CoV-2 viral load over time by RT-PCR (up to Day 28)

^a The improvement should be sustained until Day 28 (or discharge/discontinuation).^b Clinical recovery scale score worsened with at least 1 category between Day 5 and Day 28.

Objectives	Endpoints
	
 Proportion of participants with undetectable viral load (at multiple time points up to Day 28) Development of SARS-CoV-2 variants

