9.4.4. Other Secondary Endpoints

To compare the proportion of participants with an improvement of at least 1 category relative to Baseline on the 6-point ordinal clinical recovery scale relative to Baseline, the proportion of participants with a worse score relative to Baseline on the 6-point ordinal clinical recovery scale, the proportion of participants who progress to mechanical ventilation (for participants not on mechanical ventilation at baseline), and the mortality rates defined as category 6 on the 6-point ordinal clinical recovery scale, the difference in cumulative incidence at Day 28 will be estimated using the same techniques as for the key secondary endpoints.

Total length of hospitalization, total time on invasive mechanical ventilation, number of ventilation free days, and total time on ECMO will be analyzed by the stratified Wilcoxon Rank-Sum test and using the stratification factors. Corresponding 95% CIs will be derived using the Hodges-Lehmann approach.

Time to improvement of at least 1 category and other ‘time to event’ parameters will be analyzed using the stratified log-rank test.

The distribution of outcomes on the 6-point ordinal clinical recovery scale will be described via plots (eg, stacked bar plots representing the proportion of participants in each category, by treatment arm and over time).

A proportional odds model will be used to analyze the 6-point ordinal clinical recovery scale of the clinical status at Days 7, 14, 21 and 28.

Drugs used in the SOC at baseline and changes in the SOC after treatment administration will be tabulated by treatment group.

The primary and secondary endpoint evaluation will be conducted on the ITT population and on the ITT population restricted to the population with confirmed critical COVID-19 disease. Analyses of qualitative comparison between pre-interim analysis and post-interim analysis for treatment effect in the population with confirmed critical COVID-19 disease will be conducted to check the consistency in the study. This qualitative assessment will be limited to primary and key secondary endpoints only.

Other secondary parameters might be added in the SAP.

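### Ventilation-free days: the SAP scores deaths as 0 days, then describes and analyses the endpoint only in Day 28 survivors, so the death rule never acts

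*SAP*

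**What the plan says.** SAP 5.4.1 lists the endpoint as "Number of ventilation free days in participants on IMV/ECMO at baseline (up to Day 28) (days"). It is calculated as Day 28 minus the last day with a score of 5 or more on the clinical recovery scale, with a rule for deaths: "Participants who die will be considered as being on IMV/ECMO until day 28". The row contains no restriction to survivors.

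SAP 5.4.2, under duration parameters, has two sentences that do restrict it. For the summaries: "Descriptive statistics of the duration parameters will be shown for all participants that were still alive at day 28". For the analysis: "Total length of hospitalization and number of ventilation free days will be analyzed in the subgroup of participants that were still alive at day 28", using a Hodges-Lehmann approach, and then "Corresponding 90% CIs will be presented as well". No other section of the SAP analyses ventilation-free days with deaths included.

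Protocol Section 3 lists "Total length of hospitalization among the surviving participants (up to Day 28") and, next to it, "Number of ventilation free days (up to Day 28"). Survivors are named for length of hospitalization and for time to discharge, but not for ventilation-free days. Protocol 9.4.4 states that "number of ventilation free days, and total time on ECMO will be analyzed by the stratified Wilcoxon Rank-Sum test", with Hodges-Lehmann 95% confidence intervals.

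**The concern.** The definition and the analysis section contradict each other. One scores deaths as the worst possible value and the other removes them before any table or estimate is produced. Two programmers could reasonably deliver different results.

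The reading that the analysis section follows is also the weaker one. Being alive at Day 28 is determined after randomisation, and Protocol 9.2 assumes it differs by arm. If the participants who die would otherwise have been ventilated longer, a drug that saves lives keeps more of the sickest participants in its own arm and can appear to give fewer ventilation-free days. A drug that causes excess deaths can appear to give more. SAP 5.1.1 says other secondary endpoints are tested at the 1-sided 5% level, so the result would carry an inferential claim.

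The SAP also drops the protocol's named stratified test for this endpoint without giving a reason.

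**Working it through.** The documents give no power or sample size for ventilation-free days, so there is no planned figure to reproduce. The check applies the SAP's own formula and then illustrates the size of the effect.

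**1. Does the death rule reach anyone?** For a death on or before Day 28, the last day counted as ventilated is Day 28, so ventilation-free days = 28 - 28 = 0. The formula alone gives the same answer, because death is score 6 and SAP 5.2.1 carries deaths forward to Day 28. That participant is not alive at Day 28, so both sentences in SAP 5.4.2 exclude them. The number of imputed zeros that enter any output is none.

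**2. Who is removed?** At the planned rates (Protocol 9.2), deaths in the critical set are 37 × 0.40 = 14.8 on control and 74 × 0.20 = 14.8 on sirukumab. If those rates also hold in the group ventilated at baseline, the filter drops 40% of controls and 20% of sirukumab participants.

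**3. Effect on the mean.** Assumptions not in the documents:
- no drug effect on ventilation time;
- free days if alive spread evenly over 0 to 27 (ventilated on Day 1, so at most 28 - 1);
- death linked to fewer free days through a Gaussian copula with correlation r;
- the planned mortality applies to this group.

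With deaths as 0, each arm's mean is its survivor mean × (1 - mortality). For example, at r = 0.3: control 15.03 × 0.60 = 9.02, sirukumab 14.33 × 0.80 = 11.46.

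| r | Survivors only: sirukumab vs control | Difference | Deaths as 0: sirukumab vs control | Difference |
|---|---|---|---|---|
| 0 | 13.50 vs 13.50 | 0.0 | 10.80 vs 8.10 | +2.7 |
| 0.3 | 14.33 vs 15.03 | -0.7 | 11.46 vs 9.02 | +2.4 |
| 0.5 | 14.88 vs 16.08 | -1.2 | 11.91 vs 9.65 | +2.3 |
| 0.7 | 15.45 vs 17.21 | -1.8 | 12.35 vs 10.32 | +2.0 |

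With excess deaths on drug (60% against 40% on control), survivors-only shows +0.8, +1.3 and +1.8 days at r = 0.3, 0.5 and 0.7. Deaths-as-0 shows -2.7 at each.

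**4. Trial-sized samples** (4,000 simulated trials per setting, 40% vs 20% mortality, 2:1 allocation, numbers ventilated at baseline assumed, r from 0.3 to 0.7). Chance that the Hodges-Lehmann estimate falls below 0:
- 60 ventilated: 54% to 70% survivors-only, 5% to 10% with deaths as 0;
- 30 ventilated: 52% to 64% survivors-only, 13% to 18% with deaths as 0.

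With 60 ventilated, an unstratified 1-sided 5% rank-sum test favours the drug in 2.6% to 0.8% of trials survivors-only, and in 29% to 23% with deaths as 0.

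**5. A different assumption.** Suppose instead that survivors have the same distribution of free days in both arms, and that 20% to 50% of the critical set is ventilated at baseline (7 vs 15 up to 18 vs 37 participants). With 40% vs 20% mortality, the 1-sided 5% test is positive in about 4% to 5% of trials survivors-only, and in 17% to 31% with deaths as 0. Here the survivor filter introduces no bias, but it discards the mortality difference that the definition was written to count.

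**The case against.** The strongest objection is that the two passages could be reconciled the other way, by deleting the death rule and labelling the endpoint survivors-only. The plan has precedents: two neighbouring endpoints are limited to survivors, and SAP 5.2.3 analyses improvement in survivors and death as separate components. That would remove the contradiction. It would also depart from Protocol Section 3 and 9.4.4, which do not restrict this endpoint, and it would leave a comparison conditioned on survival.

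The illustration needs a reference value. At zero correlation the survivors-only estimate is already below 0 in about 43% of trials with 60 ventilated (exactly 0 in a further 15%), and in 47% with 30 ventilated (exactly 0 in 8%). The low-end figures of 54% and 52% are therefore modest shifts. The 0.7 to 1.8 day bias also compares with a standard deviation of the estimate of about 2.5 to 2.9 days (60 ventilated) or 3.7 to 4.2 days (30 ventilated). This stands and limits how much weight the figures can bear.

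Deaths-as-0 has its own weakness. With many tied zeros, the Hodges-Lehmann estimate is exactly 0 in about 30% to 33% of trials with 60 ventilated and 25% to 26% with 30. Its advantage in these scenarios comes wholly from mortality, which is already a key secondary endpoint. The two analyses answer different questions, so the gap between them is not all error.

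The 90% interval is not a fault in itself, since it matches the 1-sided 5% level in SAP 5.1.1. Protocol 9.4.3 also leaves detail on secondary endpoints to the SAP. Neither point resolves the contradiction.

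**Conclusion.** The concern holds. As written, SAP 5.4.2 makes the death rule in SAP 5.4.1 inoperative, and the resulting survivors-only comparison is not the endpoint in the protocol. The direction of the bias depends on the participants who die being those who would have been ventilated longer. Its size depends on an assumed correlation, an assumed distribution of days, and the planned mortality applying to the ventilated group. With zero correlation there is no bias, only lost information on deaths.

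The consequence is contained. This is one other secondary endpoint in a subset of participants, outside the hierarchical tests. All-cause mortality, ventilation-free survival at Day 28 and the proportional odds analysis still count deaths. It should be corrected before database lock, but it does not threaten the primary or key secondary conclusions.

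**What to change.** In SAP 5.4.2:
- Take ventilation-free days out of both survivors-only sentences.
- Analyse all participants on IMV or ECMO at baseline, with deaths as 0 days per SAP 5.4.1, by the protocol's stratified Wilcoxon rank-sum test with a Hodges-Lehmann 90% interval. The ventilation factor is nearly constant in this group, so age is in effect the remaining stratifier.
- Record the change from the protocol's 95% interval and the reason for it.
- Keep the survivors-only result as a descriptive supplement. Because ties at 0 can make the Hodges-Lehmann estimate uninformative, report the number of deaths in each arm beside it.
- State how participants who leave the study alive before Day 28 are counted. SAP 5.4.1 gives a rule for length of hospitalization but none for this endpoint, and the gap exists under the present text too.

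Extending the endpoint to participants not ventilated at baseline is a separate matter. The formula is undefined for anyone who never scores 5 or more, so a new definition would be needed.

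The cost is SAP wording only. The death rule already exists and no new data are required.
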